8.12.6. Management of hypomagnesemia, hypocalcemia, and hypokalemia

Participants will be monitored weekly for hypomagnesemia, hypocalcemia, and hypokalemia. In the event of Grade 3-4 hypomagnesemia, repletion is required as well as predosing electrocardiograms (ECG) to monitor for corrected QT (QTc) prolongation. For Grade 4 hypomagnesemia that is refractory to IV magnesium-replacement therapy, dosing with futuximab/modotuximab should be delayed or reduced. Full management instructions are provided in [Appendix 11](#).

9. OTHER ASSESSMENTS NOT SPECIFICALLY RELATED TO EFFICACY OR SAFETY

9.1. Assessments related to screening/inclusion criteria

9.1.1. Assessments related to inclusion criteria

9.1.1.1. Informed consent

Obtain signed and dated ICF from the patient during the screening visit prior to the implementation of study procedures required by the protocol. Please refer to [Section 13.3](#).

9.1.1.2. Histological/Cytological Confirmation

Histological confirmation of adenocarcinoma of the colon or rectum should be documented in the patient's source documents. The pathology report should be available in the patient's source documents.

9.1.1.3. KRAS/NRAS/BRAF status

Genomic analysis from peripheral whole blood sample for defining patient eligibility and stratification will be based on assessment of ctDNA in plasma with an oncogene panel. The sample will be submitted for mutation analysis prior to first administration of first IMP (for Safety Lead-In part) and to randomisation. The genomic analysis includes a series of genes frequently mutated in cancer, but will be focused on the following genes:

- BRAF CCI
- KRAS & NRAS CCI
- EGFR-ECD mutation analysis (for stratification purpose: "WT" if no mutation and "mutated" if one or more CCI mutations are detected).

Backup DNA extracts from included participants and screened participants non included will be stored, with the consent of the participant, for a maximum of 25 years after the end of the study according to local regulation for retrospective analysis restricted to the study of the pathology and the response to the treatment. All samples may be destroyed at any time on participant's or sponsor's request.

Additional details and the sample collection instructions are provided in laboratory manual.

9.1.2. Assessments not related to inclusion criteria

9.1.2.1. Patient Numbering (Only for Randomised part)

Once the patient has signed ICF, the study site will connect to the IWRS for patient's registration and to obtain a patient's number (see the IWRS manual for details). Each patient will be assigned a unique patient number. This patient number will be maintained throughout the study and will not be reassigned. Participants who withdraw consent or discontinue from the study after being assigned a patient number will retain their initial number.

9.1.2.2. ECOG performance status

Collect ECOG performance status score ([Appendix 2](#)).

9.1.2.3. Medical history

Obtain a complete medical history.

Of note, events occurring between the signature of the ICF and the first study treatments administration for which the investigator does not consider an association with any procedure/condition required by the study protocol must be reported as medical history in the dedicated form of the e-CRF.

9.1.2.4. Previous surgery, radiotherapy and treatments related to the colorectal cancer

Collect previous surgery, radiotherapy and treatments related to the colorectal cancer.

9.1.2.5. Baseline Signs and Symptoms

Signs and symptoms related to the colorectal cancer present following ICF signature and before the first study treatments administration should be recorded in the patient's source documents.

9.1.2.6. MMR/MSI status

MMR/MSI status will be collected in the e-CRF if available.

9.1.2.7. Demography

Collect demography data (age, sex, ethnic origin).

9.2. Measurement of drug concentration

9.2.1. Sample Collection Timepoints

Blood samples for the evaluation of PK are to be collected at the timepoints listed in [Table \(9.2.1\) 1](#) and [Table \(9.2.1\) 2](#). The accurate sampling dates and times must be recorded in the e-CRF.

Table (9.2.1) 1 - Sample collection timepoints for futuximab/modotuximab and trifluridine/tipiracil (Pharmacokinetics during the Safety Lead-In and Arm A of Randomised part)

	Futuximab and modotuximab assessment	Trifluridine and tipiracil assessment
C1D1	Pre-dose*	Pre-dose*
	End of infusion**	End of infusion**
	1-2 hours after end of infusion	1-2 hours after end of infusion
C1D8	Pre-dose*	Pre-dose*
	End of infusion**	End of infusion**
	30 min-1 hour after end of infusion	30 min-1 hour after end of infusion
C1D15	Pre-dose*	Pre-dose*
	End of infusion**	End of infusion**
	30 min-1 hour after end of infusion	30 min-1 hour after end of infusion
C1D22	Pre-dose*	Pre-dose*
	End of infusion**	End of infusion**
	30 min-1 hour after end of infusion	30 min-1 hour after end of infusion
C2D1	Pre-dose*	Pre-dose*
	End of infusion**	End of infusion**
	30 min-1 hour after end of infusion	30 min-1 hour after end of infusion
C2D8	Pre-dose*	Pre-dose*
	End of infusion**	End of infusion**
	30 min-1 hour after end of infusion	30 min-1 hour after end of infusion
C2D15	Pre-dose*	Pre-dose*
	End of infusion**	End of infusion**
	30 min-1 hour after end of infusion	30 min-1 hour after end of infusion
C2D22	Pre-dose*	Pre-dose*
	End of infusion**	End of infusion**
	30 min-1 hour after end of infusion	30 min-1 hour after end of infusion
CXD1	Pre-dose*	
WV	During the visit	During the visit

*i.e. 5-60 minutes before infusion of futuximab/modotuximab

**i.e. within 10 minutes before to the end of infusion of futuximab/modotuximab

Table (9.2.1) 2 - Sample collection timepoints for trifluridine/tipiracil (Pharmacokinetics in Arm B of Randomised part)

	Trifluridine and tipiracil assessment
C1D1	At the beginning of the visit
	At the end of the visit
C1D15	During the visit
C2D1	During the visit
C2D15	During the visit
WV	During the visit

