2.7. Clinical pharmacokinetic properties and selected dose rationale

Trifluridine is metabolized by Thymidine Phosphorylase (TPase) and transported by the nucleoside transporters CNT1, ENT1 and ENT2 while tipiracil is not metabolized (neither in human liver S9 nor in cryopreserved hepatocytes) and is a substrate for OCT2 and MATE1 transporters.⁸ As described for other monoclonal antibodies, the clearance of futuximab and modotuximab is expected to be mainly driven by TMDD as a consequence of their binding to the target EGFR and subsequent internalisation and degradation into small peptides and amino acids

Based on their non-overlapping PK properties, PK-related DDI between trifluridine/tipiracil and futuximab/modotuximab (futuximab and modotuximab) are unlikely to occur. Therefore, no dose adjustment is required when co-administered.

Overall, the proposed futuximab/modotuximab dose regimen for the study CL3-95026-001 (9 mg/kg followed by 6 mg/kg weekly dosing) was selected as the optimal dose regimen based on a benefit-risk assessment of available clinical data. In addition, the PK evaluation indicates that the target is saturated within the one-week dosing interval with this dose regimen.

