	
To further evaluate and to compare the safety profile of futuximab/modotuximab in combination with trifluridine/tipiracil versus trifluridine/tipiracil monotherapy
 
To compare Quality of life (QoL) of futuximab/modotuximab in combination with trifluridine/tipiracil versus trifluridine/tipiracil monotherapy
 
To characterise the pharmacokinetic (PK) profile of futuximab/modotuximab, trifluridine and tipiracil in the combination futuximab/modotuximab with trifluridine/tipiracil
 
To further evaluate the immunogenicity of futuximab/modotuximab (i.e. occurrence of antidrug antibody [ADA])
	
 - Incidence, severity and relationship of TEAEs and STEAEs collected from administration of the first dose of IMPs - AEs leading to dose interruption, dose delays and permanent treatment stop - Changes from baseline in key laboratory safety assessments, and vital signs - QoL is assessed by 2 questionnaires European Organization for Research and Treatment of Cancer (EORTC) QLQ-C30 and EQ-5D-5L - Derived PK parameters (e.g. Cmax, AUC) for futuximab/modotuximab, trifluridine and tipiracil 
ADA development for futuximab/modotuximab

Exploratory	
To explore the PK/pharmacodynamic (PD) relationship for safety and/or efficacy of the combination futuximab/modotuximab with trifluridine/tipiracil
 
To explore biomarkers as potential predictors of response and to track the emergence of resistance
	
 - Relationship between exposure and PD (as safety and efficacy) - Circulating tumour DNA (CtDNA) monitoring

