Amended clinical study protocol no. CL3-95026-001 – Final version

	SCR	INCL	Cycle 1				Cycle 2				Cycles 3 and after				WV within 4 weeks after treatment withdrawal and before new anticancer treatment	Follow-up period Every 8 weeks, until death or end of study	Protocol section
			D1	D8 ± 2 days	D15 ± 2 days	D22 ± 2 days	D1	D8 ± 2 days	D15 ± 2 days	D22 ± 2 days	D1	D8 ± 2 days	D15 ± 2 days	D22 ± 2 days			
QUALITY OF LIFE ASSESSMENT																	
Quality of life assessment ¹³		X					X				X				X	X	9.6

Table (4.1.2) 2 (Cont'd) - CL3-95026-001 Investigation schedule for the Randomised part

	SCR	INCL	Cycle 1				Cycle 2				Cycles 3 and after				WV within 4 weeks after treatment withdrawal and before new anticancer treatment	Follow-up period Every 8 weeks, until death or end of study	Protocol section
			D1	D8 ± 2 days	D15 ± 2 days	D22 ± 2 days	D1	D8 ± 2 days	D15 ± 2 days	D22 ± 2 days	D1	D8 ± 2 days	D15 ± 2 days	D22 ± 2 days			
LABORATORY EXAMINATIONS																	
Blood hematology ¹⁴		X	X pre-dose ⁸		X pre-dose ⁹		X		8.2.7.1								
Blood biochemistry		X	X pre-dose ⁸		X pre-dose ⁹		X		8.2.7.2								
Serum Mg, Ca, K ¹⁰			X pre-dose ⁸		X pre-dose ⁹		X		8.2.7.3								
Blood coagulation		X	X pre-dose ⁸				X pre-dose ⁹				X pre-dose ⁹		X pre-dose ⁹		X		8.2.7.4
Urinary biochemistry ¹⁵		X	X pre-dose ⁸				X pre-dose ⁹				X pre-dose ⁹		X pre-dose ⁹		X		8.2.7.5
PHARMACOKINETICS																	
Blood sample for futuximab/ modotuximab (Arm A) ¹⁶			X pre-dose*; EoI**; 1-2h after EoI	X pre- dose*; EoI**; 0.5- 1h after EoI	X pre- dose*;	X											
Blood sample for trifluridine/tipiracil (Arm A) ¹⁶			X pre-dose*; EoI**; 1-2h after EoI	X pre- dose*; EoI**; 0.5- 1h after EoI			X pre- dose*; EoI**; 0.5- 1h after EoI	X pre- dose*; EoI**; 0.5- 1h after EoI							X		9.2
Blood sample for trifluridine and tipiracil (Arm B) ¹⁶			X beginning, end of visit	X during visit		X during visit	X during visit								X		
Anti-futuximab/ modotuximab antibodies ^{10; 16}			X pre-dose*		X pre- dose*		X pre- dose*		X pre- dose*		X pre- dose*		X pre- dose* ***		X		9.5
GENOMIC ANALYSIS																	
Blood sample for ctDNA ¹⁷	X																9.1.1.3

Futuximab/modotuximab

Amended clinical study protocol no. CL3-95026-001 – Final version

	SCR	INCL	Cycle 1				Cycle 2				Cycles 3 and after				WV within 4 weeks after treatment withdrawal and before new anticancer treatment	Follow-up period Every 8 weeks, until death or end of study	Protocol section

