5.8.2. Procedure

Upon discontinuation of study treatment, the investigator must:

- Notify the sponsor immediately.
- Register the end of treatment for the patient in the IWRS for Randomised part.

- Record this information in the e-CRF, specifying the reason for the study participant's withdrawal. If there are several reasons, the investigator must indicate the main reason. The investigator should document the discontinuation in the corresponding medical file.

A withdrawal visit should always be suggested to the participant and should take place within 4 weeks after the last IMP administration and prior to the start of a new anticancer therapy.

In the case of discontinuation due to an AE (event requiring immediate notification [ERIN] or not), the investigator must make every effort to collect the information relating to the outcome of the event. If necessary, the information will be collected afterwards ([Section 8.9.2.1](#)). This information is recorded in that part of the e-CRF form which concerns AEs. If the investigator cannot collect the information from a visit, he must collect it from the doctor ensuring the follow-up of the participant.

In case of discontinuation due to an ERIN, please refer to [Section 8.7](#).

Follow-up period:

After the withdrawal visit, a follow-up will be done every 8 weeks (\pm 10 calendar days):

- For tumour assessment (unless patient had discontinued IMPs for radiologic disease progression or withdrawal of consent) until radiologic progression regardless of initiation of a new anticancer therapy.
- For survival status until death or the end of the study (whichever occur first). This follow-up can be done remotely by using various telecommunication technologies including but not limited to phone, internet and shared electronic medical records.

Participants are at any time free to discontinue their participation in the study. If participants wish to withdraw their consent to treatment period (*i.e.* both IMPs and study assessments), they will be asked if they are willing to continue with Follow-up period for survival status (which can be done by phone). If participants wish to withdraw their consent to further participation in the study entirely (treatment period and follow-up period), this should be clearly documented in the patient notes and in the clinical study database. During the post-withdrawal follow-up period, the patient can participate to another clinical trial.

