6.1.3.2. Schedule

- Trifluridine/tipiracil should be administered before futuximab/modotuximab administration.
- Trifluridine/tipiracil should only be given on Days 1 through 5 and Days 8 through 12 of each cycle. If doses are missed or held on those days, the participant should not make up for missed doses. Extension of study treatment into Days 6 to 7 or into the rest period (Days 13 through 28) is not permitted.
- Trifluridine/tipiracil should be taken with a glass of water within 1 hour after completion of morning and evening meals (or in accordance with the local SmPC of trifluridine/tipiracil).
- Any missed doses reported by the participant should be recorded in the e-CRF.
- Trifluridine/tipiracil dosage is calculated according to BSA (Body Surface Area). Table (6.1.3.2) 1 shows the number of tablets that are needed per calculated BSA for a dose of 35 mg/m². Table (6.1.3.2) 2 shows the number of tablets that are needed per calculated BSA for a reduced dose (30 mg/m², 25 mg/m² and 20 mg/m²). The BSA will be calculated by the site (in Safety Lead-In part) or IWRS (in Randomised part) using the following DuBois formula³⁰ all BSA calculations are rounded to 2 decimal places): BSA (m²) = ([Body Weight (kg)]^{0.425} x [Height (cm)]^{0.725}) x 0.007184.
- If at the beginning of the new treatment cycle, a participant's body weight decreases by $\geq 10\%$ from baseline, the site (in Safety Lead-In part) or IWRS (in Randomised part), will recalculate the participant's BSA and adjust trifluridine/tipiracil dosage.
- In case of change of dose level in Randomised part, the IWRS will provide the study site with the adjusted trifluridine/tipiracil dosage.
- No increase in trifluridine/tipiracil dose due to increase in BSA is permitted.

Table (6.1.3.2) 1 - Number of tablets of trifluridine/tipiracil per dose (standard dose) according to body surface area

Trifluridine/tipiracil Dose (2 x daily)	BSA (m ²)	Dosage in mg (2x daily)	Total daily dose (mg)	Tablets per dose (2x daily)	
				15 mg/6.14 mg	20 mg/8.19 mg
35 mg/m ²	< 1.07	35	70	1	1
	1.07 - 1.22	40	80	0	2
	1.23 - 1.37	45	90	3	0
	1.38 - 1.52	50	100	2	1
	1.53 - 1.68	55	110	1	2
	1.69 - 1.83	60	120	0	3
	1.84 - 1.98	65	130	3	1
	1.99 - 2.14	70	140	2	2
	2.15 - 2.29	75	150	1	3
	≥ 2.30	80	160	0	4

BSA = body surface area (calculate to 2 decimal places)

Table (6.1.3.2) 2 - Number of tablets of trifluridine/tipiracil per dose (reduced dose) according to body surface area

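### Three of the six Arm B trifluridine/tipiracil PK samples, including both Day 15 samples, are scheduled when the drug is not being taken

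*Protocol*

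**What the plan says.** **Sampling in Arm B.** Protocol section 9.2.1, under "Table (9.2.1) 2 - Sample collection timepoints for trifluridine/tipiracil (Pharmacokinetics in Arm B of Randomised part", sets six samples: C1D1 at the start and at the end of the visit, then one sample at some point in each of the C1D15, C2D1, C2D15 and withdrawal visits. No time relative to tablet intake is given. The Randomised-part investigation schedule (section 4.1.2) gives the Day 15 visits a window of ±2 days.

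**Dosing.** Section 6.1.3.2: "Trifluridine/tipiracil should only be given on Days 1 through 5 and Days 8 through 12 of each cycle". It adds: "Extension of study treatment into Days 6 to 7 or into the rest period (Days 13 through 28) is not permitted".

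**Withdrawal visit.** Section 5.8.2 says that it "should take place within 4 weeks after the last IMP administration".

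**Use of the data.** The Randomised-part endpoints in section 3.4 include "Derived PK parameters ( e.g. Cmax, AUC) for futuximab/modotuximab, trifluridine and tipiracil", under an objective about exposure in the combination. Section 10.3.2 plans population modelling of the concentrations, with a separate data analysis plan. On interaction, section 2.7 concludes: "Therefore, no dose adjustment is required when co-administered".

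**Sampling in Arm A.** Here the protocol is not consistent. The schedule row "Blood sample for trifluridine/tipiracil (Arm A" shows Days 1 and 8 of cycles 1 and 2, plus the withdrawal visit. The table headed "Table (9.2.1) 1 - Sample collection timepoints for futuximab/modotuximab and trifluridine/tipiracil (Pharmacokinetics during the Safety Lead-In and Arm A of Randomised part" lists trifluridine/tipiracil samples on Days 1, 8, 15 and 22.

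**The concern.** A concentration taken in the rest period says little about Cmax or AUC. Arm B is the only concurrent group that takes trifluridine/tipiracil without the antibodies, so its samples are the trial's own information on exposure to the drug alone. If half of them are timed when no drug is being taken, and the rest are not tied to intake, that information is thinner than the number of tubes suggests.

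The Day 15 timing looks as if it followed the visit calendar rather than the dosing calendar. In section 8.2.1, Arm B has vital signs only on Days 1 and 15 of each cycle. With about 250 Arm B participants (500 randomised 1:1), the two Day 15 visits would use up to 250 × 2 = 500 tubes of 4 mL.

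**Working it through.** **1. Sampling days against dosing days**
- Dosing days (section 6.1.3.2): {1-5, 8-12}.
- Day 15 ± 2 (section 4.1.2): {13, 14, 15, 16, 17}.
- Overlap: 0 of 5 days. Both Day 15 samples are in the rest period wherever the visit falls in its window.

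**2. Count of Arm B samples (Table (9.2.1) 2)**
- Total: 2 (C1D1) + 1 (C1D15) + 1 (C2D1) + 1 (C2D15) + 1 (withdrawal) = 6.
- Off drug: C1D15, C2D15 and withdrawal = 3 of 6.
- On a dosing day: C1D1 start, C1D1 end and C2D1 = 3 of 6.
- The C1D1 start-of-visit sample is presumably before the first dose, which leaves at most 2 of 6 post-dose.
- Neither of these two is guaranteed. If the C2D1 sample is drawn before intake, it follows Days 13-28, that is 28 − 12 = 16 rest days.

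The Arm B row of the schedule has shifted columns in the text read from the PDF, so Table (9.2.1) 2 is taken as the plan. It agrees with the Day 1 and Day 15 visits in section 8.2.1.

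**3. How much drug could remain**

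The documents give no half-life, so a range of 1 to 12 h is assumed. A last intake at 20:00 on Day 12 and a visit at 09:00 on day d are also assumed. Then t = (d − 12) × 24 − 11 hours, and the remaining fraction is 2^(−t/half-life).

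| Visit day | t (h) | half-life 1 h | half-life 12 h |
|---|---|---|---|
| 13 | 13 | 0.01% | 47% |
| 15 | 61 | 4 × 10^−19 | 3% |
| 17 | 109 | 2 × 10^−33 | 0.2% |

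On the nominal day at most about 3% remains under these assumptions. Only at the early edge of the window, with a long half-life, would a sample carry an appreciable level.

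**4. Arm A: 6 or 12 samples per cycle?**
- Appendix 12, cycle 1 or 2, without the trifluridine/tipiracil PK row: 20 + 10 + 20 + 10 + 5 + 5 + 30 + 5 = 105 mL.
- With 6 samples (Days 1 and 8, three each): 105 + 6 × 4 = 129 mL. This reproduces the stated 129 mL and is within the limit of under 130 mL in section 4.1.2.
- With 12 samples (Days 1, 8, 15 and 22): 105 + 12 × 4 = 153 mL. This does not reproduce the stated total and exceeds the limit.
- Over two cycles Table (9.2.1) 1 gives 8 visits × 3 = 24 samples, of which 12 are at Day 15 and Day 22 visits, in the rest period.

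**The case against.** The strongest reply accepts the calendar and disputes the harm. Most of it stands.

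- **No between-arm comparison is planned.** The PK objective concerns exposure in the combination, and the documents specify no Arm A versus Arm B contrast. A reader might infer that a drug-interaction comparison has been spoiled; none was set.
- **Exposure in combination is checked elsewhere.** Section 10.3.1 overlays lead-in concentrations on 1000 simulations of the drugs given alone, and section 4.1.3.4 also describes this assessment. It would be wrong to say that the no-adjustment statement goes wholly untested.
- **Sparse data can be used.** Section 10.3.2 plans population modelling and allows pooling with other studies. Intake times are recorded (sections 6.2 and 6.4), as are sampling times (section 9.2.1). A reader might infer that Arm B yields almost no usable exposure data, but up to two post-dose concentrations per participant could enter the model. How the data analysis plan would treat very low values cannot be seen, so damage to the model is not shown.
- **The contrast with Arm A is unsettled.** A reader might infer that Arm A is sampled only on dosing days. Table (9.2.1) 1 contradicts this, and even the Day 8 visit, with its ±2-day window, can fall on Days 6 or 7.
- **The Randomised part never ran.** The SAP introduction records its cancellation for strategic reasons, so no planned SAP analysis is affected.

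None of this gives the two Day 15 tubes a stated purpose, and none of it supplies a sampling time after intake for the other samples.

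**Conclusion.** The point holds as a limited design flaw. Both Day 15 samples in Arm B always fall in the rest period, and the withdrawal sample also comes after treatment has stopped: three of six are off drug. At most two of six can be post-dose, with neither guaranteed. The counts follow from the protocol's own calendar. The one presumption is that the C1D1 start-of-visit sample precedes the first dose. The judgement that the rest-period samples add little depends on the assumed half-life range and clock times.

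The documents do not support a larger claim, whether of a failed interaction test, a biased model or a clean contrast with Arm A. The effect is a loss of information for a secondary PK endpoint in a part of the trial that was later cancelled. It matters if the design is reused.

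The 6-versus-12 discrepancy for Arm A is a separate inconsistency. The blood-volume arithmetic agrees with 6, but a fault in reading the table from the PDF cannot be excluded.

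**What to change.** 1. In Table (9.2.1) 2 and the matching row of the Randomised-part schedule, replace the Arm B samples at C1D15 and C2D15 with one additional post-intake sample at C1D1 and one at C2D1.
2. Define the C1D1 end-of-visit and C2D1 samples by a stated time window after the recorded trifluridine/tipiracil intake. Intake times are already collected, so no new recording is needed.
3. Do not add a pre-intake sample at C2D1; it would follow 16 rest days and be no more informative than Day 15.
4. Reconcile Table (9.2.1) 1 with the investigation schedule and Appendix 12 on the number and days of Arm A trifluridine/tipiracil samples.

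**Result and cost.** C1D1 would have 3 samples, C2D1 2 and withdrawal 1, still 6 tubes and 6 × 4 = 24 mL, with the same number per cycle as now (3, then 2). Four of six samples would be post-dose by design, against at most two now. No visit is added. The price is an amendment to one table and one schedule row, and a somewhat longer Day 1 visit for Arm B.
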